### 4.3 Research question and objectives

The research question behind the study is to gain additional knowledge on safety in prophylaxis patients and obtain additional clinical data on the use of N8-GP in the setting of local clinical practice.

The primary objective of the study is to investigate the safety of N8-GP including the PEG moiety during prophylaxis and long-term use in patients with haemophilia A as prescribed by the physician.

Secondary objectives are to further evaluate the general safety of N8-GP during routine prophylaxis (including FVIII inhibitors and allergic/hypersensitivity reactions) and long-term use in patients with haemophilia A as prescribed by the physician.

Exploratory objectives are to monitor possible clinical effects of long-term exposure to N8-GP prophylaxis in patients with haemophilia A, including assessments of kidney and liver function parameters, neurological function and patients' PEG plasma level.

The primary endpoint of the study is:

- Number of Adverse Events (AEs) reported during the study period

The secondary endpoint is:

- Number of Serious Adverse Events (SAEs) reported during the study period

The exploratory endpoints are:

- Number of AEs related to hepatic or renal function during the study period
- Number of AEs that are defined within the system organ classes "Nervous system" or significant deviations from expected neurologic function during the study period
- Changes in laboratory parameters during the study period; including the hepatic and renal function parameters
- Changes in PEG-plasma levels from study start to end of study
- Number of FVIII treatment requiring bleeding episodes reported during the study period

Protocol  
NN7088-4029  
UTN: U1111-1235-6007  
EU PAS No.

~~CONFIDENTIAL~~

Date: 17 April 2020  
Version: 2.0  
Status: Final  
Page: 13 of 49

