**Novo Nordisk**

deviations from expected neurologic function during the study period

Changes in laboratory parameters during the study period, including hepatic and renal function parameters	From inclusion of the patient until end of study visit	Count of events
---	--	-----------------

PEG-plasma levels	At entry, after 2 years, and at the end of study	ng/mL
-------------------	--	-------

Number of FVIII treatment requiring bleeding episodes reported during the study period	As described in section 9.2.7.1	Count of events
--	---	-----------------

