**Novo Nordisk**

#### **9.2.7.4 PEG plasma level**

PEG plasma levels should be determined three times during the course of the study. This should preferably be done at baseline (visit 1), after two years of participation in the study and at the 'End of study visit'. Additionally, the responsible physician can request additional analyses if considered clinically warranted. The sample will be analysed at a special laboratory, contracted by sponsor, to determine the concentration of PEG in the patients' blood.

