**Novo Nordisk**

Number of these specific AEs during study period will be summarised together with the number of patients with any of these AEs. Furthermore, listings will be provided displaying all these specific AEs.

- Changes in laboratory parameters during the study period, including hepatic and renal function parameters.

Laboratory parameters will be summarised by visit. Furthermore, change from baseline (visit 1) will be summarised. Listings and individual over time profile plots (where deemed relevant) will be provided displaying laboratory parameters reported during the study period.

- PEG-plasma levels at study entry, after two years and at the end of study

PEG plasma level will be summarised by visit. Listings and individual over time profile plots will be provided displaying PEG plasma level reported during the study period.

- Number of FVIII treatment requiring bleeding episodes reported during the study period

Number of FVIII treatment requiring bleeding episodes reported during the study period will be summarised. Furthermore, listings will be provided displaying all FVIII requiring bleeding episodes.

Definition of a bleeding episode: Multiple bleeding locations occurring during the same event (e.g., due to a bicycle accident) or at the same time point will be counted as one bleeding episode. A bleeding which occurs within 72 hours after stopping treatment of a previous bleeding event at the same or a subset of the same anatomical location(s) is considered a re-bleed, and is not a new bleeding episode. If a bleeding event occurs in the same location later than 72 hours after stopping treatment of a previous bleeding event it is considered a new bleeding episode.

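### The exploratory PEG endpoint is a change in section 4.3 but a level in 9.1.3 and 9.7.2.3, and no numerical summary of within-patient PEG change is planned

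*Protocol*

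**What the plan says.** Three sections of the protocol describe the PEG endpoint.

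- Section 4.3 (Abstract): "Changes in PEG-plasma levels from study start to end of study".
- Section 9.1.3 lists PEG plasma level in ng/mL, with the time frame "At entry, after 2 years, and at the end of study".
- Section 9.7.2.3 lists "PEG-plasma levels at study entry, after two years and at the end of study".

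The planned PEG analysis, in 9.7.2.3, has two parts: "PEG plasma level will be summarised by visit" and "Listings and individual over time profile plots will be provided displaying PEG plasma level reported during the study period".

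The preceding bullet in 9.7.2.3, on laboratory parameters, also has a by-visit summary but continues: "Furthermore, change from baseline (visit 1) will be summarised". That sentence belongs to the laboratory bullet. PEG has its own bullet and its own analysis text.

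On sampling, 9.2.7.4 says that "PEG plasma levels should be determined three times during the course of the study". It gives the timing as a preference.

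**The concern.** A change from study start to end of study is a within-patient quantity, and sampling each patient three times is designed to supply it. If PEG is summarised numerically only visit by visit, a reader of the report will compare the Visit 1 figure with the end-of-study figure. That comparison equals the mean within-patient change only if the same patients contribute to both.

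The matter has some weight. Section 7 gives PEG accumulation as the reason for the study obligation, and 9.1 says the plasma measurements were requested by the EMA. A shift in by-visit means caused by a changed set of patients could be read as accumulation or clearance, and a real change could be masked.

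**Working it through.** **1. Endpoint wording against planned output**

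| Place | Quantity named | Numerical summary planned in 9.7.2.3 |
|---|---|---|
| 4.3 | Change in PEG, start to end | None |
| 9.1.3 and the 9.7.2.3 bullet | PEG level at three times | Yes, by visit |
| Laboratory parameters (9.7.2.3) | Change | Yes, by visit and as change from Visit 1 |

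The by-visit summary answers the level version. The change version has no numerical summary.

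**2. Can the sampled patients differ between visits?** Yes, for four reasons given in the protocol:

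- Section 9.2.1 plans 60 patients to be included and 50 to complete: 60 − 50 = 10, and 10/60 = 16.7%.
- Section 9.2.6 makes the flow-chart assessments other than consent non-mandatory.
- Section 9.2.7.4 states the timing of the PEG samples as a preference.
- Section 9.2.6.4 allows the end-of-study visit to be a phone contact, which yields no blood sample.

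**3. Size of the composition effect (illustration)**

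There is no figure in the plan to reproduce. The protocol gives no SD for PEG and no rate of missing samples, and 9.5 says no formal sample size calculation was made. The inputs below are therefore assumptions, apart from the 60 and 50 taken from 9.2.1. Using those two numbers as sample counts is itself an assumption.

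Let *n* of 60 patients have a final sample. Let *d* be the entry mean of the patients without a final sample minus that of the patients with one, in entry SDs. Suppose no patient's level changes, and write *m* for the mean of the *n* patients.

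- Visit 1 mean = [n·m + (60 − n)(m + d)]/60 = m + d(60 − n)/60
- End-of-study mean = m
- End minus entry = −d(60 − n)/60

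With n = 50, the absolute difference is d × 10/60:

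- d = 0.5: 0.083 SD
- d = 1.0: 0.167 SD
- d = 1.5: 0.250 SD

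If fewer final samples are obtained, the effect grows in proportion to the number missing. With d = 1.0 it is 20/60 = 0.333 SD for n = 40 and 30/60 = 0.500 SD for n = 30.

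A summary of change in the *n* patients with both samples is exactly zero in each of these cases.

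**The case against.** A reader might infer that PEG is analysed only through separate by-visit summaries, so that within-patient change cannot be seen at all. The protocol does not support that. Listings and individual profile plots are planned, and for PEG the plots are unconditional, whereas for laboratory parameters they are made only where judged relevant. Each patient's course will be visible. What is missing is a numerical summary of it.

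A reader might also infer a loss of power or precision from not pairing. That does not apply: 9.7.2 rules out hypothesis testing and limits the results to descriptive statistics, and no interval is planned for PEG.

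The best defence is that 4.3 is part of the Abstract, whose title entry still carries a draft date of 23 January 2020, while 9.1.3 and 9.7.2.3 agree with each other and the by-visit analysis fits their definition. An extra change table could also be left to a SAP. Both points have force and lower the weight of the finding. They do not remove it. The conflicting definitions stand in the final protocol, section 9.7 makes a SAP optional, and the protocol itself specifies a change summary for laboratory parameters but not for PEG.

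Three further points stand as limits:

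- The regulatory concern is PEG in organs and tissues, which plasma levels do not measure directly.
- Patients who withdraw are to be encouraged to attend an end-of-study visit, so some non-completers may give a final sample.
- Section 4.4 admits patients already exposed to N8-GP, so Visit 1 is not a PEG-free baseline for everyone.

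**Conclusion.** The point holds as an inconsistency in endpoint definition together with a missing summary. Section 4.3 promises a change, the operative sections define levels, and no planned number estimates the change. The by-visit analysis is not wrong for the endpoint as 9.1.3 words it.

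The possible misreading is 0.08 to 0.25 SD between by-visit means with no true change, if 10 of 60 patients lack a final sample and differ at entry by 0.5 to 1.5 SD. It would be larger with fewer final samples, and zero if those lost resemble those kept. Neither the number of missing samples nor the entry difference is known from the protocol, so this shows what could happen and is not a forecast. For an exploratory, descriptive endpoint the weight is minor to moderate. The remedy is close to free.

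**What to change.** Use one definition of the PEG endpoint in 4.3, 9.1.3 and 9.7.2.3. Keep the by-visit summary, listings and profile plots, and add to 9.7.2.3:

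> *Change in PEG plasma level from Visit 1 to year 2 and from Visit 1 to end of study will be summarised in patients with both samples (number of pairs, mean, SD, median, minimum, maximum), with the Visit 1 summary for the same patients.*

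Showing the Visit 1 values of the paired patients beside those of all patients sampled at Visit 1 lets a reader see any difference in composition directly.

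The cost is one sentence, an alignment of wording and one table, with no new samples or patients. The downside is a somewhat smaller n than in the by-visit table. The change table describes only patients with both samples, some of whom may have been exposed to N8-GP before Visit 1, and the report should say so.

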## 9.1 Study design

This is a prospective, multi-national, non-interventional post-authorisation study in patients with haemophilia A, prescribed prophylaxis with N8-GP by the treating physician prior to and independent of the decision to include the patient in the study. The study is designed to obtain additional real-life exposure and safety information.

The study is planned to include safety follow-up assessments at routine care visits for at least, but not limited to 5 years with 50 patients. Patients may continue in the study for the total planned study duration allowing active data collection for up to 7 years.

This study aims to observe routine use of N8-GP in any eligible patient in accordance with care prescribed by the treating physician, to the extent that enrolment of patients is allowed under local regulatory rules.

Monitoring of safety will be performed from a patient's first exposure to N8-GP after enrolment in this study defined by completion of informed consent through the patient's last visit in the study (defined as end of study or withdrawal of informed consent). Adverse events (AEs) are expected to be captured through the periodic clinical evaluations every 6-12 months that are routinely undertaken in patients with haemophilia A. Follow-up on any AE will be carried out until resolution of the AE, and if the patient discontinues to the extent allowed by IRB/ethics committees following discontinuation of the study. Exploratory assessment of the patients' PEG plasma level as requested by EMA, will be performed at pre-defined time points (see section [9.2.7.4](#)) and if considered clinically warranted by the responsible physician.

Protocol  
NN7088-4029  
UTN: U1111-1235-6007  
EU PAS No.

CONFIDENTIAL

Date: 17 April 2020  
Version: 2.0  
Status: Final  
Page: 18 of 49

Novo Nordisk

The follow up period after discontinuation of study drug should be as long as possible, preferably until end of study.

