**Novo Nordisk**

- b) Only FVIII requiring bleeding episodes must be captured including bleed details and severity rating where available.
- c) One measurement two years after enrolment and if considered clinically warranted by the responsible physician.

Informed consent is required when entering the study. The rest of the assessments listed in the flow chart are not mandatory, but it is recommended to monitor safety of N8-GP in participating patients. Information from assessments performed during the patient's participation in the study should be recorded in the eCRF from the time informed consent has been obtained. For each visit the site personnel should enter all available information in the eCRF as specified in the below sections.

Patients should receive care at their respective clinic in accordance with local clinical practices. All study visits should be performed according to local clinical practice. The physician should keep a patient enrolment log and a log of patients evaluated for, but not included in the study, throughout the enrolment period. These logs may be separate or combined in one document. Patient identification is to be accomplished via allocation of a six-digit number which consists of a three-digit site code and a three-digit patient ID. A range of numbers will be provided by Novo Nordisk.

Signed informed consent must be obtained from the patient or, for patients under legal age, from the parent(s) or LARs prior to any study related activities.

Patients enrolled in the study should be provided with contact address(es) and telephone number(s) of the physician site and/or staff. In case a patient is being prematurely withdrawn from the study the physician should ensure that the procedures for the last visit are recorded, if possible.

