### **9.2.6.4 End of study visit**

This visit will take place just prior to the planned study LPLV date. In case a patient withdraws his consent, the physician should encourage the patient to come in for an end of study visit. Relevant data regarding the assessments listed in the flow chart must be entered in the eCRF, if available.

The end of study visit may, if not possible to be conducted as an on-site visit, be performed as a phone contact. This should only be done in case a patient does not visit the site as part of his routine care.

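### The last planned PEG sample follows the study calendar rather than treatment, so the by-visit summary mixes on-drug and off-drug values and late stoppers have no on-treatment sample after year 2

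*Protocol*

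**What the plan says.** **Sampling.** Section 9.2.7.4 states: "PEG plasma levels should be determined three times during the course of the study". On timing it continues: "This should preferably be done at baseline (visit 1), after two years of participation in the study and at the 'End of study visit". The physician may ask for further samples on clinical grounds.

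**Timing of the last visit.** Section 9.2.6.4 places the end of study visit shortly before the planned last-patient-last-visit date. A patient who withdraws consent is encouraged to attend one when he withdraws. A telephone contact is allowed as a fallback: "The end of study visit may, if not possible to be conducted as an on-site visit, be performed as a phone contact". This is limited to patients who have no routine site visit.

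**Follow-up after stopping.** Section 9.1 states: "The follow up period after discontinuation of study drug should be as long as possible, preferably until end of study". Section 9.7.1 keeps every patient exposed to N8-GP during the study in the safety analysis set.

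**Analysis.** Section 9.7.2.3 states that "PEG plasma level will be summarised by visit", and adds: "Listings and individual over time profile plots will be provided displaying PEG plasma level reported during the study period". In the same section the other laboratory parameters get both a by-visit summary and a change from baseline.

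**Endpoint.** Section 4.3 lists "Changes in PEG-plasma levels from study start to end of study". Section 9.1.3 lists PEG levels in ng/mL at entry, two years and end of study.

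**Obligation to sample.** Section 9.1 presents PEG assessment as something that will happen at pre-defined times at EMA's request. Section 9.2.6, after requiring consent, says: "The rest of the assessments listed in the flow chart are not mandatory".

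**The concern.** Plasma PEG is the only direct PEG measurement in the study. Section 7 says that the study answers an obligation to investigate possible effects of PEG accumulation. The natural reading of the late PEG summary is the level reached after years of prophylaxis.

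As written, the late summary does not estimate that. The third sample is attached to a calendar visit, and patients who have stopped N8-GP are deliberately kept to that visit. Their value may have been drawn months or years after the last dose, yet it enters the same mean as values from patients still on prophylaxis. A flat or falling mean between year 2 and end of study could then reflect drug stopping rather than stable or falling levels on treatment, and a true late rise could be hidden.

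There is also a gap in the data themselves. A patient who stops between year 2 and the end of study has no planned on-treatment measurement after year 2. No later analysis can supply it.

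**Working it through.** The protocol gives no figure for this point: section 9.5 reports no sample size calculation, and nothing is stated on stopping rates or PEG clearance. The dates can be checked; the size can only be illustrated.

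**1. When the last sample falls.** From section 6, first visit is 03 June 2020 and last visit 03 June 2027, so the study lasts 7.0 years. Section 4.4 gives about 2 years of recruitment.
- Earliest entrant: 7.0 years from entry to end of study.
- Latest entrant: 7.0 − 2 = 5.0 years.
- Gap between the year 2 sample and the last sample: 5 − 2 = 3 to 7 − 2 = 5 years.

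**2. Effect of pooling.** Hold the on-treatment level flat at 100. Let f be the share of final samples drawn off N8-GP and r the fraction of PEG still in plasma then. The pooled mean is

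M = 100 × (1 − f × (1 − r)).

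Both f and r are assumptions. With 60 final samples (the planned enrolment):

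| Off drug | r = 0 | r = 0.5 |
|---|---|---|
| 3 of 60 | 95.0 | 97.5 |
| 5 of 60 | 91.7 | 95.8 |
| 10 of 60 | 83.3 | 91.7 |
| 15 of 60 | 75.0 | 87.5 |

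For 5 to 10 off drug, the shortfall runs from 100 − 95.8 = 4.2 to 100 − 83.3 = 16.7, that is about 4% to 17%. With 50 final samples (the planned completers), the same counts give 90.0 to 95.0 for 5 off drug and 80.0 to 90.0 for 10.

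**3. What could be hidden.** With r = 0, a true on-treatment rise of 1/(1 − f) − 1 would leave the pooled mean flat. At f = 10/60 this is 1/(50/60) − 1 = 20%.

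**4. Which comparison is affected.** Section 4.4 admits patients with or without earlier N8-GP, so some entry values may be near zero. Take 25% unexposed at entry (PEG 0), everyone on drug at year 2, and 10 of 60 off drug at the end with r = 0:
- entry mean 75, year 2 mean 100, final mean 83.3;
- entry to end: 83.3 − 75 = +8.3;
- year 2 to end: 83.3 − 100 = −16.7.

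The distortion therefore need not show as a fall from entry. It is clearest after year 2.

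**5. Telephone end visits.** PEG needs a blood sample, so a telephone contact leaves the value missing. With 10 of 60 off drug and r = 0:
- nobody missing: 50/60, mean 83.3;
- 10 on-drug patients missing: 40/50, mean 80.0;
- 10 on-drug and 2 off-drug missing (20% of each group): 40/48, mean 83.3;
- all 10 off-drug patients missing: 50/50, mean 100.0.

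The effect can go in either direction, or nowhere.

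**The case against.** **A statistical analysis plan may deal with this.** Section 9.7 foresees one, and a split by treatment status or a table of within-patient change could properly go there. That stands for the analysis. It does not stand for the sampling time, which the protocol fixes, or for the difference between 4.3 and 9.1.3 in what the endpoint is.

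**The protocol plans more than means.** Listings and individual PEG profiles are promised without condition, and 9.2.8.9 requires dated regimen changes and deviations from the prescribed prophylaxis to be recorded. With about 60 patients, a careful reader could see who was off drug. This limits the harm considerably, but it neither corrects the summary nor supplies a sample that was not drawn.

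**The wording on obligation is nearly consistent.** Section 9.2.7.4 is itself phrased as a recommendation, which fits 9.2.6, and 9.9 discloses the limits of routine-practice data. Only 9.1 reads more firmly, so this is a small reconciliation.

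**Stopping may be rare among those who matter.** Section 4.4 aims for 50 patients with at least 5 years of prophylaxis. If that is met, off-drug patients at the end come mainly from the other 10 or from those who stop after year 5, and some of the 10 will have left the study. Ten of 60 is then towards the upper end.

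**Stronger readings that the documents do not support.** A reader might infer that telephone visits create a false fall; they only cause missing values, and 9.2.6.4 limits them to patients without a routine site visit. A reader might also call the fall itself unreal. A lower level after stopping would be real clearance; what would be wrong is to read it as a fall under continued prophylaxis. Nor is every final sample tied to the calendar, since patients who withdraw consent are encouraged to attend then.

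**Conclusion.** The point holds in a limited form. Sections 9.1, 9.2.6.4, 9.2.7.4, 9.7.1 and 9.7.2.3, followed as written, pool on-drug and off-drug PEG values at the last visit and leave anyone who stops after year 2 without a planned later on-treatment sample. The pooled mean can then understate late levels under continued prophylaxis, chiefly from year 2 to end of study.

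The range of about 4% to 17% is an illustration. It assumes 5 to 10 of 60 final samples off drug, 50% to 0% residual PEG, a flat on-treatment level and all patients on drug at year 2. A definite bias of that size, or a fall from entry, cannot be inferred.

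Separately, the abstract names a change for which the analysis section states no summary. The endpoint is exploratory and descriptive, but it bears directly on the reason for the study. Severity is minor to moderate; confidence is medium.

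**What to change.** 1. **Section 9.7.2.3:** classify each PEG sample as on or off N8-GP from the dated regimen records, with the date of last dose noted at sampling. Summarise the two groups separately, with the on-treatment samples as the answer on long-term prophylaxis. The detail may sit in the statistical analysis plan.
2. **Sections 4.3, 9.1.3 and 9.7.2.3:** align the endpoint. Report within-patient change from entry to year 2 and from entry to the last on-treatment sample, with the number of missing samples at each visit.
3. **Section 9.2.7.4:** seek a PEG sample at or near the visit where permanent stopping of N8-GP is recorded. Keep any end of study sample as off-treatment data, since values after stopping also inform the accumulation question.
4. **Sections 9.1, 9.2.6 and 9.2.7.4:** reconcile whether the three PEG samples are expected of every patient or only recommended.

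The cost is wording, one date field and, for patients who stop, one sample triggered at a routine visit. Patients who stay on N8-GP still have three planned samples. The practical burden is that sites must recognise permanent stopping in time to draw the sample.
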